4.4 End of Study Definition	To further clarify explicitly that sites should only initiate clinical routine activities (e.g., blood drawing) after the unblinding process has been completed. To further describe that the end of study is defined as when the end of study blood laboratory testing and all other EOS-visit safety examinations have been collected/received at site and have been reviewed.	Clarification of process.
5.3.4 COVID-19 Vaccination Considerations	To give more guidance in the COVID-19 pandemic situation with regards to the different COVID-19 vaccines	COVID-19 pandemic.

Section # and Name	Description of Change	Brief Rationale
6.1 Study Intervention(s) Administration	Packaging and Labeling: Remove the sentence "The medical care treatment in the second year will be supplied in blisters containing 1, 4 and 6 tablets like the commercial split."	Clarification of process.
6.3.2 Blinding	Unblinding process after end of study for each participant: Removed "immediately".	Clarification of process.
6.7 Study Intervention after the End of the Study	Supply of cladribine treatment described.	Clarification of process.
6.9 Management of Adverse Events of Interest	Hematological monitoring: Added a sentence on lymphocytes blinding, result review, and adverse event reporting process.	Clarification of process.
7.2 Participant Discontinuation/Withdrawal from the Study	Drop-out rate and number of participants evaluable adapted to recalculated sample size.	Recalculation of the sample size.
8.2.4 Clinical Safety Laboratory Assessment	Reference added to Section 6.9 instead of reference to Medical Monitoring Plan.	Minor correction.
[REDACTED]	[REDACTED]	[REDACTED]
Appendix 4 Adverse Events: Definitions and Procedures for Recording, Evaluating, Follow-up, and Reporting	Adverse events of special interest: Explicitly express that only "lymphopenia" Grade 3/4 represents an AESI, not Grade 1 and 2. Align and clarify nonserious AESI reporting process and the AESI Reporting Form (AESIs Grade 3/4 lymphopenia to be reported)	Clarification of process.
Appendix 9 Coordinating Investigator Signature Page	Site number "CCI" added.	Completion of signature page.
Whole document	Correction of typing errors, minor editorial and document formatting revisions	Minor corrections; therefore, have not been summarized.

- Confidential -

1.1 Synopsis

Protocol Title: A randomized, double-blind, 2-period, 2-sequence crossover Phase I study with a 1 month Run-in-Period to examine the effect of cladribine tablets on the pharmacokinetics of a monophasic oral contraceptive containing ethinyl estradiol and levonorgestrel (Microgynon®) in pre-menopausal women with relapsing multiple sclerosis (RMS).

Short Title: Effects of cladribine tablets on the pharmacokinetics of Microgynon®

Rationale: The primary study rationale is to evaluate the potential effects of cladribine tablets on the pharmacokinetics of an oral contraceptive (Microgynon tablets [ethinyl estradiol (EE) 30 µg, levonorgestrel (LNG) 150 µg]).

Objectives and Endpoints:

Objectives	Endpoints (Outcome Measures)	Endpoints (Outcome Measures) Timeframe
Primary		
To examine the effect of repeat-dose cladribine tablets on the repeat-dose pharmacokinetics of the monophasic oral contraceptive Microgynon by assessment of its constituents, ethinyl estradiol (EE; 30 µg/tablet) and levonorgestrel (LNG; 150 µg/tablet)	
 Primary PK parameters calculated for EE and LNG from plasma concentrations: Area under the concentration–time curve from zero to tau at steady state ($AUC_{\tau,ss}$), and the maximum plasma concentration at steady state ($C_{max,ss}$). Secondary PK parameters calculated for EE and LNG: $C_{min,ss}$; C_{trough}; $t_{max,ss}$; $C_{av,ss}$; and peak-to-trough fluctuation (PTF%). 	Study Periods 1 and 2 on Days 14/15
Secondary		
To examine the safety and tolerability of Microgynon and cladribine co-administration.	Occurrence of treatment-emergent adverse events (TEAEs), changes in safety laboratory tests, 12-lead electrocardiograms (ECGs) (morphology, and time intervals [PR, QRS, RR, QT and corrected QT intervals [QTc]), and vital signs (PR, SBP, DBP, body temperature)	Time from first treatment to last assessment
To examine cladribine exposure	Cladribine C_{max} and t_{max}	Cladribine PK sampling in Study Periods 1 and 2 at predose on Days 9, 10, 11, 12 and 13, postdose on Days 10, 11, 12 and 13 at 0.25, 0.5, 1.0, 1.5, 2.0h

ss =at steady state; AUC_{τ} =Area under the concentration–time curve from zero to tau; C_{av} =average concentration; C_{max} =maximum plasma concentration; C_{min} =minimum observed concentration during a complete dosing interval; C_{trough} =concentration observed immediately before next dosing; DBP=diastolic blood pressure; ECG=electrocardiogram; EE=ethinyl estradiol; h=hour; LNG=levonorgestrel; PK=pharmacokinetic; PTF%=peak-to-trough fluctuation; PR=pulse rate; QTc=corrected QT intervals; SBP=systolic blood pressure; t_{max} =time to reach the maximum observed concentration collected during a dosing interval; TEAEs=treatment-emergent adverse events

Overall Design: This is a randomized, double-blind, 2-period, 2-sequence crossover study with a 1 month Run-in-Period in pre-menopausal women with active relapsing multiple sclerosis (RMS) requiring a disease-modifying RMS treatment. The study design will comprise a ≤ 21 -day Screening period followed by a Microgynon Run-in-Period, followed by 2 sequential treatment periods (Study Periods 1 and 2) of 28 days each. In case the Screening period lasts > 21 days and ≤ 60 days due to a delayed menstrual cycle of the participant (Run-in Day 1), it is acceptable that the participant starts delayed with the Run-in-Period without having re-performed the Screening assessments. In case of the requirement to re-assess one or more Screening laboratory value(s), the Screening period may be prolonged for up to 8 weeks after the last Screening laboratory assessment and it is acceptable that the participant starts with a delayed Run-in-Period without re-assessing the complete set of Screening laboratory assessments.

[figure not shown]
Number of Participants: CCI [REDACTED]

Study Intervention Groups and Duration: In the Run-in-Period as well as during both treatment periods, Microgynon will be administered for 21 days, followed by 7 days off-treatment. In Study Periods 1 and 2 Microgynon will continue to be administered together with randomized treatment sequences of a 5-day once-daily cladribine treatment in Study Period 1 followed by a 5-day placebo treatment in Study Period 2, or vice versa; i.e., participants will be randomized to 1 of 2 double-blind treatment sequences, either cladribine-placebo or placebo-cladribine.

Involvement of Special Committee(s): No.

1.2 Schema

Figure 1 Study Design Diagram

CLA=Cladribine tablets, 10 mg; MGY=Microgynon tablets (Ethinylestradiol 30 µg, Levonogestrel 150 µg); PLC=Cladribine Placebo tablets; D=day; PK=blood sampling for pharmacokinetics.

1.3 Schedule of Activities

- The Schedule of Activities (SoA) is provided below.

Schedule of Activities – Screening, Run-in-Period and Study Period 1

Assessments & Procedures	Screening (up to 21 days before Day 1) ^b	Run-in- Period	Intervention Study Period 1 (Days)									Notes	
			D 1 to 28	D 8	D 9	D 10	D 11	D 12	D 13	D 14	D 15		D 21
Residency				X	X	X	X	X	X	X	X		In individual cases Investigator may allow participants to stay overnight at home from Day 8 to Day 12. In-patient stay is required from the evening of Day 13 until discharge on Day 15 after completion of all planned study assessments.
Ambulatory Visit	X	X										X	Run-in-Period: ambulatory visits on Days 7, 14 and 21
Written Informed Consent	X												Prior to any screening procedures
Inclusion and Exclusion Criteria review	X			X ^a									a Re-check before administration on: contraception method, blood loss and lifestyle considerations. Results of safety laboratory on Day 21 of Run-in-Period (Baseline).
Demographic Data	X												
Physical Examination	X												
Herpes Zoster Serology	X												Serology diagnosis, if ABS negative vaccination and at least 4 weeks before cladribine administration
Medical History / Concomitant Disease	X												
Prior and Concomitant Treatment	X	X	X	X	X	X	X	X	X	X	X	X	

Assessments & Procedures (cont'd, Study Period 1)	Screening (up to 21 days before Day 1) ^b	Run-in- Period D 1 to 28	Intervention Study Period 1 (Days)									Notes
			D 8	D 9	D 10	D 11	D 12	D 13	D 14	D 15	D 21	
Hematology, Clinical Chemistry & Urine Analysis	X	X								X		Run-in-Period on Day 21 (Baseline)
QuantiFERON®-TB Test	X											Done in local laboratory
Serum Pregnancy Test	X											
Urine Pregnancy Test		X	X									A negative urine pregnancy test must be in place at Day 7 of Run-in-Period and on Day 8 of Study Period 1.
Alcohol Breath Test / Drugs of Abuse	X		X									See Appendix 5 . On Day 8 urine drug screen is done locally
Height / Weight / Body Mass Index (BMI)	X	X									X	Additional weight control: Run-in-Period on Day 21 and on Day 21 Study Period 1
Vital Signs	X	X		X	X	X	X	X	X			Run-in-Period on Days 7, 14 and 21. Days 9-13 predose and 1 h postdose; on Day 14 at 24 h and 25.5 h postdose (Day 13) of cladribine/placebo administration
12-lead ECG	X			X						X		On Day 9 predose and 1.5 h postdose; on Day 14 at 24 h and 25.5 h postdose (Day 13) of cladribine/placebo administration
Randomization		X										Within 10 days after Run-in-Period Day 21
Participant Diary Delivery	X	X									X	
Microgynon Delivery	X	X									X	During Screening a second appointment needs to be scheduled to deliver Microgynon after lab values for inclusion have been assessed.
Participant Diary Collection		X									X	Run-in-Period on Day 21

Assessments & Procedures (cont'd, Study Period 1)	Screening (up to 21 days before Day 1) ^b	Run-in-Period D 1 to 28	Intervention Study Period 1 (Days)										Notes
			D 8	D 9	D 10	D 11	D 12	D 13	D 14	D 15	D 21		
Empty Microgynon Packing Collection		X											Run-in-Period on Day 21
Administration of Microgynon		Daily D1 to D21	Daily intake D1 to D21										Microgynon should be taken at the same time between 7:00 ante meridiem (a.m.) and 9:00 a.m.
Fasting (≥ 10 h before visit)	X			X	X	X	X	X					≥ 10 h before cladribine / placebo administration and at least 1 h postdose
Standardized Meals / Beverages			X	X	X	X	X	X	X				
Administration of Cladribine / Placebo				X	X	X	X	X			X		Between 8:00 a.m. and 10:00 a.m. after overnight fasting. Participants will receive cladribine/placebo on Days 15-19 of Study Period 1 as well to keep the blinding.
PK Blood Sampling EE and LNG		X							X	X	X		Run-in-Period on Days 7, 14 and 21 in the morning (ambulatory visit). On Day 13 in the morning (predose of Microgynon administration); on Day 14 predose and at 0.5, 1, 2, 4, 6, 8, 12, and 24 h (Day 15) postdose
PK Blood Sampling Cladribine				X	X	X	X	X					On Day 9 predose of cladribine/placebo administration; on Days 10-13 predose and at 0.25, 0.5, 1, 1.5 and 2.0 h postdose of cladribine/placebo administration
CCI													
Adverse Events	X	X	X	X	X	X	X	X	X	X	X	X	Recording of Adverse Events starts at signature of Informed Consent

- a See information given in the 'notes column' for line 'inclusion and exclusion criteria review.
- b In case the Screening period lasts > 21 days and ≤ 60 days due to a delayed menstrual cycle of the participant (Run-in Day 1), the participant can start with a delayed Run-in-Period without having re-performed the Screening assessments. In case of the requirement to re-assess one or more Screening laboratory value(s), the Screening period may be prolonged for up to 8 weeks after the last Screening laboratory assessment and the participant can start with a delayed Run-in-Period without re-assessing the complete set of Screening laboratory assessments.

Schedule of Activities – Study Period 2 and End of Study

Assessments & Procedures	Intervention Study Period 2 (Days)									End of Study	Notes
	D 8	D 9	D 10	D 11	D 12	D 13	D 14	D 15	D 21	4-7 days after completion of D21	
Residency	X	X	X	X	X	X	X	X			In individual cases Investigator may allow participants to stay overnight at home from Day 8 to Day 12. In-patient stay is required from the evening of Day 13 until discharge on Day 15 after completion of all planned study assessments.
Ambulatory Visit									X	X	
Physical Examination										X	
Prior and Concomitant Treatment Review	X	X	X	X	X	X	X	X	X	X	
Hematology, Clinical Chemistry & Urine Analysis		X					X			X	
Urine Pregnancy Test	X									X	A negative urine pregnancy test is required prior to cladribine administration on Day 9.
Alcohol Breath Test / Drugs of Abuse	X										See Appendix 5 Urine drug screen is done locally
Weight / BMI	X									X	
Vital Signs		X	X	X	X	X	X			X	On Days 9-13 predose and 1 h postdose; on Day 14 at 24 and 25.5 h postdose (Day 13) of cladribine/placebo administration
12-lead ECG		X					X			X	On Day 9 predose and 1.5 h postdose; on Day 14 at 24 h and 25.5 h postdose (Day 13) of cladribine/placebo administration
Participant Diary Collection										X	

Assessments & Procedures (cont'd, Study Period 2)	Intervention Study Period 2 (Days)									End of Study 4-7 days after completion of D21	Notes
	D 8	D 9	D 10	D 11	D 12	D 13	D 14	D 15	D 21		
Empty Microgynon Packing Collection										X	
Administration of Microgynon	Daily intake D1 to D21										Microgynon should be taken at the same time between 7:00 a.m. and 9:00 a.m.
Fasting (≥ 10 h before visit)		X	X	X	X	X					≥ 10 h before cladribine/ placebo administration and at least 1 h postdose
Standardized Meals / Beverages	X	X	X	X	X	X	X				
Administration of Cladribine / Placebo		X	X	X	X	X			X		Between 8:00 a.m. and 10:00 a.m. after overnight fasting. Participants will receive cladribine/placebo on Days 15-19 of Study Period 2 as well to keep the blinding.
PK Blood sampling EE and LNG						X	X	X			On Day 13 in the morning (predose of Microgynon administration); On Day 14 predose and at 0.5, 1, 2, 4, 6, 8, 12, and 24 h (D15) postdose
PK Blood Sampling Cladribine		X	X	X	X	X					On Day 9 predose of cladribine/placebo administration; on Days 10-13 predose and at 0.25, 0.5, 1, 1.5 and 2.0 h postdose of cladribine/placebo administration
CCI											
Adverse Events	X	X	X	X	X	X	X	X	X	X	

2 Introduction

Cladribine is a prodrug, which is activated after intracellular phosphorylation to 2-chlorodeoxy-adenosinetriphosphate (CdATP). Cladribine through its active metabolite exerts reversible selective depletion of lymphocytes, which are thought to underlie the autoimmune processes involved in multiple sclerosis (MS) pathophysiology.

In August 2017, cladribine tablets were granted marketing authorization by the European Commission (EC) for the treatment of highly active relapsing multiple sclerosis (RMS) in the 28 countries of the European Union (EU) and additionally in several further countries. Complete information on the chemistry, pharmacology, efficacy, and safety of cladribine is in the Investigator's Brochure and Package Insert and Summary of Product Characteristics ([Merck Serono Europe Ltd., 2017](#)).

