Appendix 5 Clinical Laboratory Tests

Clinical laboratory tests utilized for the study are shown in the table below.

Table 8 Protocol-Required Clinical Laboratory Assessments

Laboratory Assessments	Parameters			
Hematology	Platelet Count		RBC Indices: 
 • MCV • MCH • %Reticulocytes 	WBC Count with Differential: 
 • Neutrophils • Lymphocytes • Monocytes • Eosinophils • Basophils
	RBC Count			
	Hemoglobin			
	Hematocrit			
Clinical Chemistry	BUN	Potassium	Aspartate aminotransferase (AST) / serum glutamic-oxaloacetic transaminase (SGOT)	Total and direct bilirubin
	Creatinine	Sodium	Alanine aminotransferase (ALT) /serum glutamic-pyruvic transaminase (SGPT)	Total Protein
	Glucose (fasting)	Calcium	Alkaline phosphatase	Uric acid
	Amylase	Lipase	γ-Glutamyl-transferase	Triglycerides
	Lactate dehydrogenase	Creatine phosphokinase	Urea	LDL-/HDL-cholesterol and cholesterol
Urinalysis	
 • Specific gravity • pH, glucose, protein, blood, ketones, bilirubin, urobilinogen, nitrite, leukocyte esterase by dipstick • Microscopic examination (if blood or protein is abnormal). Only if blood, protein, nitrite, or leukocyte esterase are positive on the dipstick • Urine pregnancy test (as needed for women of childbearing potential) 			
Other Tests	
 • Serum human chorionic gonadotropin (hCG) pregnancy test (as needed for women of childbearing potential). • Serology (HIV 1 and 2 antibody (anti-HIV1/2), hepatitis B surface antigen (HbsAG), hepatitis B core antibody (HbcAb), hepatitis C virus (anti-HCV) and Herpes Zoster • QuantifERON®-TB Gold or Gold Plus test • Alcohol breath test, • TSH • Urine drug screen: 
 • Cocaine • Amphetamines • Methamphetamines • Opiates • Barbiturates • Ecstasy • Benzodiazepine • Methadone • Cannabinoids • Phencyclidine • Tricyclic antidepressants 			

ALT=alanine aminotransferase; AST=aspartate aminotransferase; BUN=blood urea nitrogen; HbcAB=hepatitis B core antibody; HbsAG=hepatitis B surface antigen; hCG=human chorionic gonadotropin; HCV=hepatitis C virus; HDL=high density lipoprotein; HIV=human immunodeficiency virus; LDL=low density lipoprotein; MCH=mean corpuscular hemoglobin; MCV=mean corpuscular volume; RBC=red blood cell; SGOT=serum glutamic-oxaloacetic transaminase; SGPT=serum glutamic-pyruvic transaminase; TSH = thyroid stimulating hormone, WBC=white blood cell

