15.3 Clinical Laboratory Evaluation

The following treatment labels will be used in tables and listings:

- Screening: During the screening period
- Run-in Period: During run-in period

- Microgynon + Placebo or Microgynon + Cladribine: For the measurement on Day 8, Day 9 and Day 14
- Follow-up: During follow-up/end of study period

All laboratory data will be reported with SI units. Laboratory parameters will be listed by subject and time-point and summarized indicating the treatment at the respective time-point using descriptive statistics and Box and Whisker plot for absolute values and change from baseline over time by treatment sequence, period and treatment.

Laboratory values that are outside the normal range will also be flagged in the data listings, along with corresponding normal ranges. Clinically significant abnormalities/outliers as per the Toxicity Grading Scale for Healthy Adult and Adolescent Volunteers Enrolled in Preventive Vaccine Clinical Trials will additionally be listed separately. Clinically significant values will be defined as values with toxicity grading of grade 2 or higher.

'Baseline' refers to the last scheduled measurement before administration of cladribine or placebo on Day 9 of each period. I.e. 'baseline' for period 1 refers to assessments on Day 21 of the run-in period.

Shift tables for post-dose shift (Low, Normal, High, Missing) will also be presented. The shift tables will be presented for follow-up versus screening.

See Appendix 5 of the clinical study protocol for a table of the safety laboratory evaluations.

Safety laboratory values are separated into:

- Hematology
- Biochemistry
- Urinalysis
- Other tests

Descriptive statistics shift tables and box plots will be created only for hematology and biochemistry results.

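### Table 8 asks for fasting glucose, but no fast is scheduled at End of Study, the visit that the SAP shift tables set against a fasted Screening

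*Protocol*

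**What the plan says.** Protocol Appendix 5, Table 8, includes "Glucose (fasting" in the clinical chemistry panel, with no restriction by visit. "Triglycerides" is in the same panel without a fasting qualifier. Protocol 8.2.4 has the Appendix 5 tests drawn at the times in the Schedule of Activities and gives no fasting instruction of its own.

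In the Schedule of Activities (Protocol 1.3), the row "Hematology, Clinical Chemistry & Urine Analysis" is marked at both Screening and End of Study. The fasting row is headed "Fasting (≥ 10 h before visit". In the first table it is marked at Screening and on Days 9 to 13, with the note "≥ 10 h before cladribine / placebo administration and at least 1 h postdose". In the second table it is marked on Days 9 to 13 only, with the matching note "≥ 10 h before cladribine/ placebo administration and at least 1 h postdose", and the End of Study cell is empty. End of Study is timed as "4-7 days after completion of D21".

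SAP 15.3 uses the follow-up label for the end-of-study period, limits shift tables to hematology and biochemistry, and fixes the comparison: "The shift tables will be presented for follow-up versus screening".

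**The concern.** The appendix and the schedule give a site different instructions for the same blood draw. A site that follows the schedule has no reason to ask the participant to arrive fasted at End of Study, while Table 8 presumes that she does.

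This matters because of what the SAP does with the sample. Glucose and triglycerides both respond to recent food. If some women eat before End of Study and all fast before Screening, part of any move from Normal to High reflects breakfast. Changes in safety laboratory tests are a named secondary endpoint, and a shift table that ends after treatment invites a drug interpretation. There is no placebo group at that visit against which to judge it.

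**Working it through.** No formula or sample-size figure is involved, and the plan states no number to reproduce. The check sets the passages side by side.

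1. **Where End of Study falls.** Microgynon is taken on Days 1 to 21 of each cycle, followed by 7 days off (Protocol 4.1 and 6.6.3). The visit is 4 to 7 days after Day 21: 21 + 4 = 25 and 21 + 7 = 28. It therefore lies on Days 25 to 28, inside the tablet-free Days 22 to 28.

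2. **Whether another fasting rule covers it.** Section 6.6.3 ties an overnight fast to taking Microgynon, and no Microgynon is taken on Days 25 to 28. Section 6.6.1 requires a fasted state for cladribine or placebo on Days 9 to 13 and 15 to 19, and the last of these is before Day 25. Sections 5.3.1 and 8.2.4 contain no fast for laboratory samples.

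3. **The two visits compared by the shift tables.**

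| Item | Screening | End of Study | Source |
|---|---|---|---|
| Chemistry drawn | Yes | Yes | Protocol 1.3 |
| Fasting row | Marked | Blank | Protocol 1.3 |
| Microgynon or cladribine/placebo taken that morning under the protocol | No | No | Protocol 4.1, 6.6.1, 6.6.3 |
| Glucose labelled fasting | Yes | Yes | Protocol Table 8 |
| Role in the shift table | Reference | Post-treatment | SAP 15.3 |

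4. **Whether the Fasting row concerns dosing only.** Its note does, but its heading refers to the visit, and it is marked at Screening, where no study drug is given. The schedule thus asks for a fast at one non-dosing visit with chemistry and not at the other. The evidence is the blank End of Study cell; the wording of the note does not mention that visit.

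5. **Whether a placebo comparison could separate food from drug.** The cladribine-placebo sequence receives cladribine on Days 9 to 13 of Period 1 and Days 15 to 19 of Period 2. The placebo-cladribine sequence receives it on Days 9 to 13 of Period 2 (Protocol 4.1). Every participant who completes dosing has had cladribine before End of Study, so there is no such comparison.

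6. **Whether the SAP compensates.** SAP 15.3 has no fasting flag and no rule for samples of unknown fasting status.

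**The case against.** The strongest reply is that Table 8 already settles the matter. Section 8.2.4 sends the Appendix 5 tests to the scheduled visits, and Appendix 5 calls glucose fasting, so read literally a fasting sample is specified at End of Study too. This has force. A reader might infer that the End of Study samples are unfasted, and the documents do not show that. They show an inconsistency that leaves fasting status uncontrolled. The separate Lab Manual, which is not among these documents, might also give a fasting instruction; the schedule and Table 8 would still need to agree.

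A reader might also infer that the laboratory baselines are mismatched, because Run-in Day 21 and Day 14 have no fasting mark while Period 2 Day 9 has one. The documents do not support this. Run-in Day 21 and Day 14 are tablet mornings, and Section 6.6.3 already requires an overnight fast before the tablet between 7:00 and 9:00. Section 4.1 makes Run-in Day 21 a morning visit with trough sampling. The clock time of the safety draw is not fixed, but a difference in fasting status is not established.

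It is also fair to say that the shift table could not isolate cladribine even with perfect fasting, since it spans three Microgynon cycles as well. The cladribine-placebo contrast in laboratory values rests on the period summaries, and Section 8.2.4 has a physician judge each abnormality individually. These points limit the consequence. They do not make Screening and End of Study comparable for glucose.

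**Conclusion.** The point stands as a minor inconsistency with a practical consequence. For glucose, the schedule and Table 8 disagree at End of Study, and the SAP's shift comparison depends on that visit. For triglycerides there is no contradiction with Table 8, only the same lack of comparability.

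The exposure is every Screening to End of Study pair for glucose and, as a comparability matter, for triglycerides. A reader might want to turn this into a number of women with a spurious shift to High. The documents give no rate at which food moves values above the limit, and the participant number is blacked out, so no such count is supported.

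Only descriptive safety tables are affected. The four primary pharmacokinetic comparisons do not use these data. The conclusion assumes that sites follow the Schedule of Activities and that no document outside the protocol and SAP imposes a fast at End of Study.

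**What to change.** - **Protocol 1.3:** mark the End of Study safety blood draw as fasting, so that the schedule agrees with Table 8. Run-in Day 21 and Day 14 need no new mark on this account.
- **eCRF:** record fasting status for the safety blood sample.
- **SAP 15.3:** flag glucose and triglyceride values of unconfirmed fasting status in the shift tables, with a footnote. Keep the values in the tables; removing safety results is unnecessary when a flag tells the reader what to discount. This step also works for samples already taken.

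The cost is one schedule mark, one eCRF field and one SAP footnote. For the participant it means one more overnight fast before a morning visit.
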